### 3.2. Rationale for Study Design and Control

**Study Design:** This is a multicenter, randomized, open-label, Phase 3 study designed to demonstrate that hyperpolarized  $^{129}\text{Xe}$  gas MRI is equivalent to  $^{133}\text{Xe}$  scintigraphy for the evaluation of pulmonary function. The vast differences in technique for obtaining hyperpolarized  $^{129}\text{Xe}$  MRI as compared to  $^{133}\text{Xe}$  scintigraphy make it impossible to blind study procedures. However, all image interpretation will be performed by personnel blinded to the subject's medical history and all study assessments ([Section 5.5](#)).

**Dose:** Dose justification is provided in [Section 5.3.2](#) for hyperpolarized  $^{129}\text{Xe}$  and in [Section 5.3.3](#) for  $^{133}\text{Xe}$ .

**Population Choice:** The proposed study population includes subjects requiring imaging evaluation of pulmonary function prior to lung resection surgery. Subjects being considered for surgery normally undergo a full pulmonary evaluation to provide regional lung function information used for surgical decisions.

**Control:** Regional lung function information is used for making decisions regarding the need for, and predicted success of, resection surgery. Current practice for pre-operative evaluation employs nuclear scintigraphy methods using  $^{133}\text{Xe}$  ventilation and/or Technetium ( $^{99\text{m}}\text{Tc}$ )

perfusion (the V/Q scan). This permits the patient's post-operative FEV1 to be estimated based on the amount of function that will be removed by resection surgery. For the purposes of this study,  $^{133}\text{Xe}$  will be used as the comparator to evaluate the performance of hyperpolarized  $^{129}\text{Xe}$  in patients being considered for lung resection surgery.

### 3.3. Study Duration and Dates

Subjects are expected to participate in this study for a maximum of 15 days unless the subject undergoes resection surgery. For the subset of subjects undergoing surgery, the maximum study participation is expected to be 4 months.

## 4. STUDY POPULATION SELECTION

### 4.1. Study Population

This study will include subjects who are being evaluated for possible lung resection surgery. For the purposes of this study, lung resection surgery will include segmentectomies, lobectomies, and pneumonectomies. Specific inclusion and exclusion criteria are provided below.

At least 32 subjects will be enrolled in the study. Subjects will be recruited primarily via cardiothoracic surgeons for enrollment at 2 clinical sites in the US.

### 4.2. Inclusion Criteria

Subjects will be eligible for participation in the study only if they meet ALL of the following criteria:

1. Male or female subjects  $\geq 18$  years of age.
2. Subject is being evaluated for possible lung resection (e.g., segmentectomy, lobectomy, or pneumonectomy).
3. Subject is able to undergo MRI imaging and able to fit in the MRI coil.
4. Subject is willing and able to comply with all study procedures.
5. Subject must understand and voluntarily sign an informed consent form (ICF) prior to any study-specific assessments or procedures.

### 4.3. Exclusion Criteria

Subjects will not be eligible for participation in the study if they meet ANY of the following criteria:

1. Baseline blood oxygen saturation ( $\text{SpO}_2$ )  $< 90\%$  at rest (refer to [Section 6.3.2](#)). For patients requiring routine supplemental oxygen,  $\text{SpO}_2$  measurements should be taken with the patient's normal oxygen supplementation.

2. Female subjects of childbearing potential with a positive serum pregnancy test at screening, or who are not taking (or not willing to take) acceptable birth control measures through the Follow-up Period. Adequate birth control methods include with a monogamous partner who was sterilized more than 6 months prior to screening, or measures with a Pearl index of  $<1$  used consistently and correctly (including intrauterine devices, or implantable, injectable, oral, or transdermal contraceptives). Women are not considered to be of childbearing potential if they meet at least 1 of the following 2 criteria as documented by the Investigator:
  - They have had a hysterectomy, bilateral salpingectomy, or bilateral oophorectomy at a minimum of 1 menstrual cycle prior to signing the ICF; or
  - They are post-menopausal: for women  $\geq 55$  years of age, defined as  $\geq 1$  year since their last menstrual period, or for women  $< 55$  years of age, defined as  $\geq 1$  year since their last menstrual period and have a follicle-stimulating hormone (FSH) level in the laboratory's normal range for post-menopausal phase.
3. Women who are lactating and insist on breast feeding.
4. Subjects who have received any other investigational therapy within 4 weeks prior to Screening.
5. Subjects who require anesthesia or heavy sedation to undergo MRI testing. Mild sedation could be acceptable (i.e. a low dose oral acting anxiolytic medication such as alprazolam) as long as, in the opinion of the investigator, the subject meets Inclusion Criteria #4 and #5.

## 5. STUDY TREATMENTS

### 5.1. Description of Treatments

#### 5.1.1. Study Drug

The study drug is hyperpolarized  $^{129}\text{Xe}$  gas generated from gas cylinders containing Xe/He/N2 (Section 6.9.1).

#### 5.1.2. Active Comparator

The active comparator (reference standard) is  $^{133}\text{Xe}$  gas.

### 5.2. Treatments Administered

#### 5.2.1. Study Drug

Up to 750 mL hyperpolarized  $^{129}\text{Xe}$  gas will be inflated with ultra-high purity nitrogen (N2) gas to a final volume of 1 L. To ensure that each dose has sufficient polarization ( $>10\%$ ), the polarization level will be measured at the Polarization Measurement Station within 5 minutes prior to administration.

The hyperpolarized  $^{129}\text{Xe}$  gas (in  $\text{N}_2$ ) will be administered to the subject while in the MRI scanner. Subjects will be required to inhale the 1 L of gas mixture and hold their breath for a maximum of 15 seconds (generally 10-15 seconds, based on the length of the scan) while the MRI is administered.

If the resulting scan is determined, or thought to be, inadequate, then a calibration dose (approximately 100 mL hyperpolarized  $^{129}\text{Xe}$  gas) will be administered followed by another full ( $\leq 750$  mL) dose. The calibration dose will be administered to allow for adjustments of MRI parameters, as needed, to ensure best image quality. If calibration is required, subjects will be exposed to hyperpolarized  $^{129}\text{Xe}$  for a maximum of 45 seconds.

During the MRI session, one or more conventional proton MRI scans will be collected to confirm lung anatomical features. Subjects will be required to take a full inhalation breath of room air and hold their breath for a maximum of 15 seconds while the MRI is acquired.

Detailed information for preparation and administration of hyperpolarized  $^{129}\text{Xe}$  gas is provided in the [IMP Handling and Labeling Instruction Manual](#) for this study.

#### 5.2.2. Active Comparator

The active comparator,  $^{133}\text{Xe}$ , will be administered by inhalation from a closed respirator system or spirometer in accordance with the Package Insert. Subjects will be exposed to  $^{133}\text{Xe}$  gas for 3-4 minutes as tolerated.

Detailed information for preparation and administration of  $^{133}\text{Xe}$  is provided in the [IMP Handling and Labeling Instruction Manual](#) for this study as well as the  $^{133}\text{Xe}$  Package Insert.

### 5.3. Selection and Timing of Dose for Each Patient

#### 5.3.1. Timing for Performing Scans

Imaging should be performed within the established 48 hour window (refer to the Schedule of Events in [Appendix 1](#)).

#### 5.3.2. Hyperpolarized $^{129}\text{Xe}$ Dose Selection

Since this is a diagnostic drug-device combination, dosing is performed only at the time of imaging. To ensure that each dose has sufficient polarization ( $>10\%$ ) for imaging, the polarization will be measured within 5 minutes prior to administration.

The dose range for hyperpolarized  $^{129}\text{Xe}$  for this study was calculated based on a typical fast gradient echo image acquisition signal-to-noise ratio (SNR) and voxel volumes from studies conducted to date. The calculated hyperpolarized  $^{129}\text{Xe}$  dose equivalent is 75 mL in order to provide scans with adequate SNR. This dose equivalent represents the product of Xe volume,

isotopic enrichment, and polarization. Assuming polarization levels  $>10\%$  and isotopically enriched  $^{129}\text{Xe}$  at  $\sim 85\%$ , the calculated Xe volume for evaluation is  $\leq 750$  mL.

Information regarding safety and nonclinical evaluations of hyperpolarized  $^{129}\text{Xe}$  is provided in the [IB](#).

### 5.3.3. $^{133}\text{Xe}$ Dose Selection

$^{133}\text{Xe}$  will be dosed according to the Package Insert. Please refer to the [IMP Handling and Labeling Instruction Manual](#) for additional details.

### 5.4. Method of Assigning Subjects to Treatment Groups

All randomized subjects will be divided between 2 treatment orders in a 1:1 ratio. Subjects will be randomized to receive either  $^{129}\text{Xe}$  followed by  $^{133}\text{Xe}$ , or  $^{133}\text{Xe}$  followed by  $^{129}\text{Xe}$ . All subjects will receive at least 1 dose of hyperpolarized  $^{129}\text{Xe}$  and 1 dose of  $^{133}\text{Xe}$  during study participation.

### 5.5. Blinding

This is an open-label study (refer to [Section 3.2](#) for rationale).

Images generated from this study will be interpreted by central readers blinded to the subject's medical history and all study assessments. The images will be uploaded in a blinded manner to a computer for review. Both  $^{133}\text{Xe}$  scintigraphy and hyperpolarized  $^{129}\text{Xe}$  MRI will be quantified using commercially available software.

### 5.6. Concomitant Therapy

There are no restrictions with respect to concomitant therapies for this study. All concomitant medications should be listed in the electronic case report form (eCRF) along with the date therapy was initiated, and if applicable, terminated.

For patients taking inhalers, there are no restrictions with respect to timing of dose and imaging. However, the last dose administered prior to imaging should be recorded on the eCRF.

For patients requiring supplemental oxygen, there are no restrictions with respect to timing of dose and imaging. However, the oxygen flow rate should be recorded on the eCRF.

### 5.7. Restrictions

There are no restrictions for this protocol with respect to prior therapies, or food and fluid intake.

#### 5.8. Treatment Compliance

Site personnel will administer both hyperpolarized  $^{129}\text{Xe}$  and  $^{133}\text{Xe}$  while the subject is at the site. All administration information will be recorded on the eCRF.

#### 5.9. Packaging and Labeling

Polarean will provide each of the 3 components of the device (Hyperpolarizer, Polarization Measurement Station, and Gas Delivery Bag) to the site. Gas cylinders containing the Xe/He/N2 gas blend and the ultra-high purity N2 gas will be provided to the site from a commercial vendor. All cylinders will have normally required labeling upon site receipt.

Labeling instructions for the hyperpolarized  $^{129}\text{Xe}$  in the Gas Delivery Bag are provided in the [IMP Handling and Labeling Instruction Manual](#).

#### 5.10. Storage and Accountability

The components of the device (Hyperpolarizer and Hyperpolarization Measurement Station) will be stored in an area located in a separate area (or room) close to the MRI suite.

The Investigator (or delegate) will maintain accountability records for the receipt, dispensing, and return of all study products (including the gas cylinders used to make the study drug). Records will include (but not limited to):

- The receipt of the gas cylinders to be used for study drug preparation;
- Updated inventory of the gas cylinders, and
- The return of empty or unused cylinders.

#### 5.11. Investigational Product Retention at Study Site

During and at the end of the study, the number of gas cylinders will be reconciled against current inventory and dispensing records as part of routine monitoring visits. After reconciliation, unused (full) gas cylinders will be returned to the Sponsor.

Additionally, during and at the end of the study, the use of tedlar bags, tubing, and mouth pieces will be reconciled against current inventory and dispensing records as part of routine monitoring visits. Items that have been used should be disposed of in a biohazard bag. After reconciliation, all unused components will be returned to the Sponsor.

## 6. STUDY PROCEDURES

The Schedule of Assessments is provided in [Appendix 1](#). All assessments and treatments are to be performed either at a hospital or in a doctor's office.

## 6.1. Informed Consent

Written informed consent must be obtained from each subject or legal representative (if subject is unable to sign) after the nature of the study has been fully explained in accordance with International Conference on Harmonization (ICH) Good Clinical Practices (GCP). Informed consent must be obtained prior to performing any study-specific procedures.

## 6.2. Demographics, Medical History, and Concomitant Medications

Demographic information (age, race, gender, weight, height, smoking history, etc.) will be collected during the Screening Period. Medical history, including significant medical conditions, pulmonary function values, and surgical history, will also be collected during the Screening Period. Additionally, any medications taken as well as baseline signs and symptoms occurring within 2 weeks of screening will be recorded.

On the day(s) of the Imaging Period, any changes to the subject's condition that affect inclusion/exclusion criteria will be documented, as well as any additional medications taken. Subject must meet all inclusion/exclusion criteria upon entering the Imaging Period.

## 6.3. Vital Signs

Vital signs will include blood pressure (BP, systolic and diastolic measurements), heart rate (HR), respiration rate, blood oxygen saturation ( $\text{SpO}_2$ ) and temperature. Vital signs will be assessed during the Screening Period as well as before and after each scanning session (both  $^{129}\text{Xe}$  and  $^{133}\text{Xe}$ ) during the Imaging Period. Subjects will have a 5-minute rest in a supine position before vital signs are assessed.

The subject will be monitored for the duration of the MRI exam by qualified medical professionals.

### 6.3.1. Heart Rate

HR will be assessed during the Screening Period as well as before and after each scanning session (both  $^{129}\text{Xe}$  and  $^{133}\text{Xe}$ ) during the Imaging Period. Changes in HR of  $>20\%$  are considered significant. The next dose of any study treatment will not be administered until the HR is within 20% of the baseline value. If the subject has received their last dose, they will be observed until the HR is within 20% of the baseline value.

### 6.3.2. Blood Oxygen Saturation

$\text{SpO}_2$  will be assessed during the Screening Period as well as before (within 5 minutes) and after (within 1 minute) each scanning session (both  $^{129}\text{Xe}$  and  $^{133}\text{Xe}$ ) during the Imaging Period. An absolute decrease of  $\text{SpO}_2$  by  $>10\%$  is considered significant. The next dose of any study treatment will not be administered until the  $\text{SpO}_2$  is within 10% of the baseline value. If the

subject has received their last dose, they will be observed until the  $\text{SpO}_2$  is within 10% of the baseline value.

If the subject's  $\text{SpO}_2$  value does not return to within 10% of the baseline value within a few minutes (2-5 minutes), supplemental oxygen should be provided until values are within range. Once the value is within range, the subject can proceed to the next dose.

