**Figure 2 Depiction of the Hyperpolarization Process and Device Components**

The system functions by attaching a gas cylinder containing the Xe/He/N2 gas blend to the Hyperpolarizer. This system hyperpolarizes high purity, inert,  $^{129}\text{Xe}$  gas, which is collected as a solid in a cryogenic trap (a cold finger), then thawed, and dispensed into a 1 L delivery bag.

After dispensing an appropriate volume of Xe into the bag (based on dose required, e.g., full or calibration dose), the remaining bag volume is filled with ultra-high purity N2 buffer gas. Afterwards, the degree of  $^{129}\text{Xe}$  hyperpolarization is measured with the Polarization Measurement Station. The gas sample can be temporarily stored on the Polarization Measurement Station platform until it is needed for patient administration. To ensure that each

dose has sufficient polarization, the polarization will be measured within 5 minutes prior to administration to ensure the value is  $>10\%$ .

Additional information for preparation and administration of hyperpolarized  $^{129}\text{Xe}$  gas are provided in [Section 5.2.1](#) as well as the [IMP Handling and Labeling Instruction Manual](#) for this study.

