 SpO2 is measured at baseline as well as before and after each scanning session (both Xe and Xe). An absolute decrease of SpO2 by greater than 10% is considered significant. If the subject is to receive another dose, the next dose will not be administered until the SpO2 is within 10% of its baseline value. If the subject has received their last dose, they will be observed until the SpO2 is within 10% of its baseline value. The subject will be monitored for the duration of the MRI exam by a qualified medical professional.

 Subjects will be monitored for any subjective sensation of residual anesthesia (e.g., lightheadedness, loss of sensation or awareness, loss of memory, or unconsciousness). If the subject is to receive another dose, the next dose will not be administered until the sensation has resolved. If the subject has received their last dose, they will be observed until the

sensation has resolved. The subject will be monitored for the duration of the MRI exam by a qualified medical professional.

 Eligibility assessment will include, if applicable, a negative pregnancy test.

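### The rule that releases the next dose sets no minimum SpO2 and no recheck at the usual oxygen flow, so a further oxygen-free 129Xe breath is allowed at 80 / 85 / 88% for a baseline of 90 / 95 / 98%

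*Protocol*

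**What the plan says.** **The release rule.** Protocol 6.3.2 treats an absolute SpO2 fall of more than 10% as significant and withholds the next dose of either product until SpO2 is back within 10% of baseline. If it has not recovered in 2-5 minutes, supplemental oxygen is given until it is in range. Then: "Once the value is within range, the subject can proceed to the next dose". Footnote 7 of Protocol Appendix 1 repeats the hold, until SpO2 "is within 10% of its baseline value", and SAP 11.1 carries the same footnote. Neither footnote mentions rescue oxygen.

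**The entry limit.** Exclusion criterion 1 (Protocol 4.3) bars a resting SpO2 below 90%. For patients on routine oxygen, the reading is taken on their "normal oxygen supplementation". Protocol 6.2 applies the criteria once more at the start of imaging: "Subject must meet all inclusion/exclusion criteria upon entering the Imaging Period".

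**What the next dose can be.** Protocol 5.2.1 allows more than one 129Xe dose in a session: "If the resulting scan is determined, or thought to be, inadequate, then a calibration dose" is given, followed by a second full dose. Under Protocol 5.4 ("All randomized subjects will be divided between 2 treatment orders in a 1:1 ratio"), one order has 129Xe second, so even its first 129Xe breath is a next dose. The bag description in Protocol 6.9.1 covers both dose sizes: "based on dose required, e.g., full or calibration dose), the remaining bag volume is filled with ultra-high purity" nitrogen. No oxygen is listed in the bag.

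**The concern.** The sponsor chose 90%, on the patient's usual oxygen, as the lowest saturation at which a subject may start imaging. Minutes later the release rule may let the same subject start another oxygen-free breath, held for up to 15 seconds, at a lower value. Because the rule is relative to baseline, the lowest permitted values go to the subjects who began with the lowest saturation.

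Rescue oxygen adds a second gap. A value that came into range on added oxygen does not show what the saturation is at the subject's usual flow, and 6.3.2 asks for no further reading before dosing.

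What is at stake is subject safety around further 129Xe doses. Release to 133Xe is outside this point: that gas is "administered by inhalation from a closed respirator system or spirometer" (Protocol 5.2.2), and the present rule for it can stay.

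**Working it through.** The plan states no release value to reproduce, so the check is direct arithmetic on the rule.

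**Inputs**
- Significant fall: more than 10, absolute (Protocol 6.3.2; footnote 7). A fall of exactly 10 is therefore in range.
- Entry limit: 90% (Protocol 4.3), so eligible baselines run from 90 to 100%.
- Candidate floors F: 88% (proposed) and 90% (the protocol's own entry limit).

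**Formulas**
- Present limit = baseline − 10. If the 10% in the release sentence is read as relative, it is 0.90 × baseline.
- Limit with floor = max(F, baseline − 10).
- Permitted fall = baseline − limit with floor.

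| Baseline SpO2 (%) | Present limit | Relative reading | Limit, floor 88 | Permitted fall, floor 88 | Limit, floor 90 | Permitted fall, floor 90 |
|---|---|---|---|---|---|---|
| 90 | 80 | 81.0 | 88 | 2 | 90 | 0 |
| 92 | 82 | 82.8 | 88 | 4 | 90 | 2 |
| 95 | 85 | 85.5 | 88 | 7 | 90 | 5 |
| 98 | 88 | 88.2 | 88 | 10 | 90 | 8 |
| 100 | 90 | 90.0 | 90 | 10 | 90 | 10 |

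**Results**
1. At baselines of 90 / 95 / 98% the present limit lies 10 / 5 / 2 points below the entry limit. Only a baseline of 100% keeps release at 90%. The relative reading moves these values by at most 1 point and does not change the conclusion.
2. Baseline cannot exceed 100, so baseline − 10 never exceeds 90. A 90% floor would make the baseline condition redundant and leave a baseline-90 subject no permitted fall.
3. With an 88% floor, the baseline condition still sets the limit above a baseline of 98%, and a baseline-90 subject keeps a 2-point allowance.

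**The reading after rescue oxygen.** The usual-flow instruction stands in exclusion criterion 1. Section 6.3.2, which gives the rescue oxygen and then releases the subject, names no flow for the releasing value and asks for no later one.

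**The case against.** **A rule exists, and the threshold is a clinical choice.** A 10-point fall stops dosing of either product, and nothing in the documents shows that one short breath-hold from 85% or 88% is unsafe. The entry limit also serves a different purpose from recovery between doses. This stands: the documents do not determine the right floor, which is why the clinicians should set it. They still give no floor at all.

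**Other safeguards exist.** Qualified staff monitor the whole MRI exam, heart rate and residual anesthesia have their own holds, and drug can be stopped or the subject withdrawn. The wording allows dosing and does not compel it. All true, but the only SpO2 number staff are given for this decision is relative to baseline.

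**The usual-flow point may be covered.** Exclusion criterion 1 cross-refers to 6.3.2 and could be read as governing its readings, and giving oxygen until values are in range can mean that it stops there. Both readings are fair. But the criterion speaks only of routine oxygen users, and even if oxygen stops, no reading afterwards is required.

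**Prior exposure is reassuring.** Protocol 1.5 reports 103 people exposed with no TEAEs. But 55 were healthy volunteers, 27 had asthma and 20 had COPD, and no desaturation rate is given.

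**Stronger inferences that the documents do not support.** A reader might infer that SpO2 goes unread between doses within one MRI session, because 6.3.2 times routine readings by session. However, Protocol 8.4.3 and SAP 4.1.4 call for vital-sign monitoring around each dose, Protocol 6.3 counts SpO2 as a vital sign, and the hold itself works dose by dose. A reader might also count every possible release to a 129Xe dose and take the total as the size of the problem. That counts opportunities, including subjects who never desaturate.

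**Conclusion.** The point holds. In the text available, release to a further 129Xe breath depends on a baseline-relative limit alone. It permits 80 / 85 / 88% for baselines of 90 / 95 / 98%, and no reading at the usual flow is required after rescue oxygen.

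These are the lowest values the rule allows, not values expected in practice; 80% needs a baseline exactly at the entry limit and a full 10-point fall. The figures rest on reading 10% as percentage points. The number of subjects who would be released below 90% cannot be estimated. The handling manual, to which administration detail is delegated, is not available, so a floor set there cannot be ruled out.

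The current rule does not affect alpha, power or the primary estimate. This is a cheap safety improvement, not a flaw in the analysis.

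**What to change.** In Protocol 6.3.2, and in footnote 7 of Protocol Appendix 1 and SAP 11.1, state:

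> No further 129Xe dose, including a calibration or repeat dose, is given unless SpO2, read before that dose at the subject's usual oxygen flow (room air if none), is no more than 10 percentage points below baseline and not below [floor]. After rescue oxygen, both limits must be met again at the usual flow. If they are not, no further 129Xe is given in that session; the scan may be rescheduled within the 48-hour window.

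The sponsor's clinicians should set the floor. A suitable value is 88%. If they prefer 90%, the rule should be written as a flat 90% limit, because the baseline condition then never applies.

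**Cost.** One paragraph and two footnotes. Some subjects will wait longer, and a few repeat MRIs may be lost, mostly in subjects with low saturation. A lost repeat leaves an inadequate MRI and could remove the subject from the Efficacy Analysis Set (SAP 4.2.1). Replacement is not certain, because Protocol 3.1 replaces those who discontinue and this subject has both images. Rescheduling and the 88% floor limit such losses.

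The effect of such losses on power depends on the endpoint (paired 95% CI, true difference 0):
- **Protocol FEV1 endpoint, margin 0.30 L.** If 0.32 L is the SD per method, the SD of the difference is 0.32 × √2 = 0.4525 L, and 32 / 31 / 30 / 28 pairs give 90.5 / 89.3 / 87.8 / 84.5%. The √2 is an assumption, but it reproduces the planned 90% at both n = 15 (SD 0.21 L) and n = 32. If 0.32 L is already the SD of the difference, power is 99.8% with 32 pairs and 99.5% with 28.
- **SAP primary endpoint, margin 14.7%.** With 8.3% per method (SAP section 3), the SD of the difference is 8.3 × √2 = 11.7%, and power stays above 99.9% down to 24 pairs.
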